5.2.1. Tipping Point Analysis

The MI paradigm, as proposed by Rubin, does not require nor assume any specific assumption about the nature of the missing data. Further, imputations can be (theoretically) created under any assumption of missing mechanism. A sensitivity analysis will be conducted using the tipping point approach to evaluate the robustness of the primary analysis with multiple imputation under the MAR assumption. With the tipping point approach, several additional multiple imputation datasets are created, each departing slightly from the original assumptions used in the primary analyses. The intended result is to establish a certain point in which the new shifted imputations have “tipped”, or overturned, the original conclusions from the primary analysis (i.e. a statistically significant result is now not statistically significant). The magnitude of the shift required to tip the analysis are then evaluated for plausibility; an implausible shift will lead to the conclusion that the multiple imputation analysis is robust to the departure from MAR assumption.

Tipping point analysis will be conducted only for the dose group(s) that is/are statistically significant under the MAR assumption. Based on the SM04690 Phase I study, the placebo change in WOMAC pain from baseline was observed at -3.5 points. When scaled to the NRS format, this translates to a -8.75 reduction in WOMAC pain. The primary analysis will be reassessed by shifting the mean change in WOMAC pain in the treatment group by intervals of +0.5 until the historical placebo threshold of -8.75 (or the placebo response observed in SM04690-OA-02, whichever is more conservative) is reached and/or surpassed. Intervals of +0.1 may further be explored in order to determine a more precise shift parameter for the tipping point. An implausible shift parameter is defined as one that results in the magnitude of change in WOMAC pain in the treatment group to equal or worse than historical (or SM04690-OA-02, again whichever is more conservative) placebo change.

Imputations for the tipping point analysis will be performed with a seed of 201610142.

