5.2. Handling of Missing Data

Multiple imputation will be utilized for the primary and secondary analyses. Missing data will be imputed based upon the observed data for each outcome under the missing at random (MAR) assumption following the paradigm first developed by Rubin (Schafer 1999). The imputation will adjust for the outcome’s baseline data in a regression model with data imputed independently for each timepoint; any missing baseline data will also be imputed. A total of 10 imputation datasets will be created and analyzed based upon accepted convention (Schafer 1999). Error estimates of the multiple imputation itself as well as an overall summary of the efficacy analysis will be averaged across the 10 imputed datasets based upon Rubin’s paradigm.

Specifically, let Q denote the imputed mean of an efficacy outcome Y subject to missing data at a given timepoint, where the estimate of that mean for any i^{th} imputation would be defined as function of both observed and missing data such that

$$\widehat{Q}^{(i)} = E\left(Q^{(i)} | Y_{observed}, Y_{missing}^{(i)}, Y_{Baseline}, I(Group)\right), i = 1, \dots, 10.$$

After all 10 datasets have been imputed, the overall estimate of Q is a simple average defined as

$$\bar{Q} = \frac{\sum_{i=1}^{10} \widehat{Q}^{(i)}}{10}.$$

For this analysis using 10 imputed datasets, the variance of \bar{Q} is defined as

$$Var(\bar{Q}) = 1.1B + \bar{U}$$

where B is the between imputation variance and U is the within imputation variance:

$$B = \frac{1}{9} \sum_{i=1}^{10} (\widehat{Q}^{(i)} - \bar{Q})^2;$$

$$\bar{U} = \frac{\sum_{i=1}^{10} U^{(i)}}{10}.$$

Imputations will be performed with a seed of 201610141.

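### The tipping-point analysis redraws its imputations under a new seed, so its shifts do not start from the reported primary result and the tipping point can be off by several grid steps

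*SAP*

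**What the plan says.** SAP 5.2 specifies multiple imputation under missing at random (MAR) for the primary and secondary analyses: "A total of 10 imputation datasets will be created and analyzed based upon accepted convention". It fixes the random draws: "Imputations will be performed with a seed of 201610141".

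SAP 5.2.1 describes the sensitivity analysis. It says that "several additional multiple imputation datasets are created, each departing slightly from the original assumptions used in the primary analyses" and names a different seed: "Imputations for the tipping point analysis will be performed with a seed of 201610142". A result has tipped when "a statistically significant result is now not statistically significant". Entry depends on the primary draws: "Tipping point analysis will be conducted only for the dose group(s) that is/are statistically significant under the MAR assumption". The shift proceeds "by intervals of +0.5 until the historical placebo threshold of -8.75", or to the placebo change seen in this trial if that is more conservative. A finer grid is optional: "Intervals of +0.1 may further be explored in order to determine a more precise shift parameter for the tipping point". Robustness is then judged by whether the shift needed is implausibly large.

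The section does not say that the primary imputed datasets are re-used, lists no unshifted run under the second seed, and makes no allowance for Monte Carlo error.

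**The concern.** A tipping point answers one question: how far must the imputed values move before the reported conclusion changes? That requires the starting point to be the reported result. Here the shift and the random draws change together, so the distance is measured from a result that is not the reported one.

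A dose group enters only if it was significant under the first seed. One that was just significant may then appear to tip at a very small shift because the redraw was less favourable. The opposite can also happen: a favourable redraw makes a fragile result look robust. What is at stake is the credibility of the robustness statement for Week 13 WOMAC pain, not the test itself.

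**Working it through.** **Inputs from the documents.** 10 imputations and the two seeds (SAP 5.2, 5.2.1). About 445 subjects randomized 1:1:1:1, so 445/4 ≈ 111 per arm (SAP 2.1). On the 0-20 scale: baseline SD 3, final SD 4, correlation 0.1, changes of -5.8 and -3.5 (SAP 2.1). The NRS pain subscore has 5 questions scored 0-10, so it runs 0-50 (SAP 3.2.1). Multiplying by 2.5 gives SDs of 7.5 and 10 and a difference of 2.3 × 2.5 = 5.75. Tests are two-sided (SAP 8.1.1) at 0.05 (SAP 8.2.1).

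**Assumptions.** 5-20% missing per arm, and shifts applied only to imputed treated values. SAP 5.2.1 speaks of shifted imputations but also of shifting the treatment group's mean change, so the second assumption is a reading.

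**The plan's own figures.** Rubin's multiplier is 1 + 1/10 = 1.1, as stated. The rescaled placebo change is -3.5 × 50/20 = -8.75, as stated.

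**Effect of the redraw.** For two independent sets of M imputations, the SD of the difference in z is about √(2 × FMI / M), taking the fraction of missing information (FMI) as the missing rate. At 10%: √(2 × 0.10 / 10) = 0.14. Simulating the SAP's imputation model (regression on baseline and group, 10 imputations, Rubin pooling) gave 0.16.

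**Effect of one step.** The standard error of the difference is about 10 × √(1 - 0.1²) × √(2/111) × √(1/0.9) = 1.41, with the 10% value used throughout. Shifting a fraction f of the arm by 0.5 moves z by 0.5f/1.41. At 10%: 0.05/1.41 = 0.036.

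| Missing (assumed) | Redraw SD of z, formula | Redraw SD of z, simulated | z per +0.5 step | Simulated SD in +0.5 steps | Formula SD × 1.41 / f, in points |
|---|---|---|---|---|---|
| 5% | 0.10 | 0.11 | 0.018 | 0.11/0.018 ≈ 6 | 2.8 |
| 10% | 0.14 | 0.16 | 0.036 | 0.16/0.036 ≈ 4 | 2.0 |
| 15% | 0.17 | 0.21 | 0.053 | 0.21/0.053 ≈ 4 | 1.6 |
| 20% | 0.20 | 0.25 | 0.07 | 0.25/0.07 ≈ 4 | 1.4 |

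A +0.1 step moves z by a fifth as much (0.007 at 10%), so there the redraw is worth about 2.0/0.1 = 20 fine steps.

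**If the whole treated arm were shifted instead,** one +0.5 step would move z by 0.5/1.41 = 0.35 and a +0.1 step by 0.07. The redraw SD of 0.11-0.25 would then be less than one +0.5 step, but still about 1.6 to 3.6 of the +0.1 steps.

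**Chance that the redraw alone loses significance** (zero shift, 10 imputations, simulated):

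| Primary P | 5% missing | 10% | 15% |
|---|---|---|---|
| 0.04-0.05 | 31% | 38% | 44% |
| 0.03-0.04 | 11% | 20% | 24% |
| 0.02-0.03 | 0.4% | 5% | 9% |

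A repeat simulation over 5-20% missing gave 29-46%, 7-26% and 2-14% for the three rows.

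**At the first planned shift, +0.5.** For P 0.03-0.04, about 9-35% of trials tip under the new seed and 0% when the primary draws are re-used. The 0% is as expected: P = 0.04 is z = 2.05, a gap of 0.09 from 1.96, and one step covers at most about 0.07. For P 0.04-0.05 the gap is below 0.09, and 17-68% tip at +0.5 even with the primary draws.

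**Among all significant results,** seed-only loss of significance is about 0.2-0.9% at the assumed effect (5.75 points) and about 3-9% at an effect with roughly 50% power.

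**The case against.** The strongest reply is that the seed is not the root cause. A second seed matters only because 10 imputations are noisy, and re-using the primary draws makes zero shift match the primary result by construction, whether or not those draws were lucky. This largely stands. At 10% missing, going to 100 imputations with different seeds cuts the redraw SD from 0.16 to 0.05 and the loss of significance for P 0.03-0.04 from 20% to 1%. For P 0.04-0.05 it still leaves 22%, whereas re-using the draws gives zero at any number of imputations. The anchoring error and the Monte Carlo error are separate, and the second seed adds the first to the second.

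A reader might infer that a significant result can tip with no departure from MAR at all. The SAP plans no unshifted run under the second seed, so a seed-driven tip would appear at +0.5: a small departure, not none. A reader might also infer that any such tip is false. For P 0.04-0.05 that does not follow, since many of those results tip at +0.5 on the primary draws too and would be called fragile either way.

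Both seeds are pre-specified, so nothing here suggests selective choice. If the second seed is restarted for every shift, the shifted runs share their draws and differ from the primary by one common offset. The search is then orderly, but still starts in the wrong place.

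**Conclusion.** The point holds as a minor flaw in how the sensitivity analysis is anchored. Under 5-20% missing data and shifts applied to imputed treated values only, the redraw is worth about four to six +0.5 steps (one SD), in either direction. The tipping point is therefore imprecise whatever the primary P value, and the +0.1 refinement offers precision the method does not have. If the whole treated arm were shifted, the error would be smaller than one +0.5 step, though not smaller than the +0.1 grid.

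False loss of significance is a borderline problem: rare at the assumed effect (about 0.2-0.9% of significant results) and modest at roughly 50% power (about 3-9%). It would be wrong to conclude that the trial's efficacy conclusions depend on the second seed. H1 to H21 in SAP 8.2.1 are not decided on the tipping-point analysis, and SAP 5.1 rules out any adaptation after the interim.

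**What to change.** In SAP 5.2.1, replace the sentence naming the second seed. State that the shifts are added to the imputed values of the treated group in the primary analysis's imputed datasets (seed 201610141), and that the series begins with a zero-shift run that must reproduce the primary estimate, standard error and P value. This also settles which values are shifted.

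The cost is a sentence or two before the interim unblinding; no new data or design change is needed. The downside is that the anchoring error goes but the Monte Carlo error of 10 imputations does not: both analyses then share it. Only more imputations reduce that error. If the number is raised, it should be raised for the primary analysis too, so that the two remain the same datasets.

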5.3. Baseline

Baseline is defined as the last value recorded for any given parameter prior to study medication injection. However, for radiographs used to evaluate JSW, baseline is defined as the assessment prior to study medication injection with the best image quality as determined by the imaging vendor, where applicable. If two or more radiographs are assessed with the same image quality, the earliest radiograph will be considered for baseline.

5.4. Early Termination

If a subject discontinues the study, early termination assessments will be performed according to the protocol. If these assessments occur within the window of a scheduled visit (± 3 days for Weeks 4, 13 and 39 and -10 days for Week 26), they will be associated with that visit for the purposes of ITT and mITT analysis. All other visits will be considered missing data and treated as described in section 5.2.

6. STUDY SUBJECTS

6.1. Disposition of Subjects

Subject disposition will be presented in a summary table detailing the number and percentage of subjects who were consented, randomized, treated, completed the study or discontinued (e.g. screen failure, subject decision, etc.) by treatment group and site. The disposition for individual subjects will be listed along with additional information on discontinued subjects.

6.2. Demographic and Baseline Characteristics

Demographic and baseline characteristics, including gender, race, ethnicity, age, weight, height, body mass index (BMI), Kellgren-Lawrence (KL) grade, presence of bilateral OA and

Widespread Pain Index (WPI) score will be summarized by treatment group and listed for individual subjects.

6.3. Medical History

Medical history will be collected at screening and reassessed at the Week 52 (EOS) / Early Termination visit to record any changes. A summary of reported medical history will be provided by system category for each treatment group. A subject-level listing will provide further information on each event.

6.4. Protocol Deviations

For SM04690-OA-02, a protocol deviation is defined as any change, divergence or departure from the study design or procedures of a research protocol that is under the Investigator's control and that has not been approved by the site's Institutional Review Board.

Deviations are summarized into one of the following categories:

- Those who were randomized to the study even though they did not satisfy the eligibility criteria
- Those who developed withdrawal criteria during the study but were not withdrawn
- Those who received the wrong treatment or incorrect dose
- Those who received an excluded concomitant treatment
- Those who missed or received an incorrect protocol procedure

Deviations are categorized as major or minor.

- A major deviation is defined as a divergence from the protocol that materially (a) reduces the quality or completeness of the data, (b) makes the informed consent inaccurate, or (c) impacts a subject's safety, rights or welfare.
- A minor deviation is defined as a divergence from the protocol that deviates from the procedures and guidelines outlined in the protocol, but is not classified as a major deviation (i.e. the deviation does not materially (a) reduce the quality or completeness of the data, (b) make the informed consent inaccurate, or (c) impact a subject's safety, rights or welfare).

Protocol deviations will be summarized by site, category and classification, and listed for each subject.

7. SAFETY EVALUATION

The analysis of safety outcome measures will be performed on the Safety Analysis Set. The interim report will include all available safety information up to and including Week 26. The final report will include a cumulative assessment safety.

7.1. Treatment-Emergent Adverse Events

TEAEs will be presented in an overview summary table depicting the number and percent of subjects in each treatment group experiencing TEAEs by seriousness and toxicity grade severity. While all TEAEs will be considered as related to study product, the investigator's assessment of relatedness will be included in the summary table for informational purposes. TEAEs will also be summarized by MedDRA system organ class and preferred term, including the number of TEAEs and the number and percent of unique subjects experiencing each TEAE.

Separate subject-level listings will be provided for all serious and non-serious TEAEs.

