3.3. Investigational Product

3.3.1. Rationale for Dosages and Dosing Regimen

A phase 1 clinical trial was conducted to assess the safety, tolerability, pharmacokinetics (PK), and pharmacodynamics (PD) of a SM04690 formulation at 3 different dose-level concentrations (0.03, 0.07, and 0.23 mg per 2 mL injection) injected into the intra-articular space of the OA-affected target knee. The initial dose level of SM04690 (0.03 mg) was based on the mammalian species most sensitive to SM04690 in 8-week toxicology studies (the approximate residence time of the drug) in accordance with US Food and Drug Administration (FDA) guidelines. Preclinical studies to date have not demonstrated toxicity or systemic exposure at the biologically efficacious dose, so doses were selected that bracketed the projected biologically efficacious dose based on preclinical studies, hence resulting in the escalation sequence of 0.03, 0.07, and 0.23 mg per 2 mL injection.

As of 07 July 2015, 61 subjects have been enrolled in 3 ascending dose cohorts of approximately 20 subjects per cohort. Per protocol, data from cohort 1 and 2 were unblinded following the safety review of all subjects enrolled in the cohort (observed for a minimum of 12 weeks). Cohort 3 data remains blinded.

A total of 28/61 subjects have reported 68 treatment emergent adverse events (TEAEs) with 35 preferred terms. The system organ class (SOC) most reported was 'Musculoskeletal and connective tissue disorders' with 11/61 subjects reporting 19 TEAEs of 5 preferred terms.

As of 07 July 2015, following dosing in all three cohorts, there have been two dose-limiting toxicities (DLTs) and 1 serious adverse event (SAE) reported on the trial. A DLT of increased knee pain was reported and met the DLT criteria of increased pain at the target joint of greater than 30 mm increase on the pain VAS; this DLT was due to a procedural error and considered unrelated to study drug. A DLT of tachycardia paroxysmal was also reported and met the DLT criteria of an AE deemed by the investigator to be a severe or serious AE. This DLT also met

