5. CLINICAL ASSESSMENTS

5.1. Collection of Adverse Events Data

Data regarding treatment-emergent adverse events (TEAEs) will be collected in this study. TEAEs are events that occur during the course of the study that are not present prior to Day 1 study medication injection, or, if present at the time of study medication injection, have worsened in severity during the course of the study. Adverse events will be assessed at each study visit from the time of study medication injection on study visit Day 1 through Week 52 (EOS)/Early Termination.

Each subject will be observed and queried by the Investigator or the Investigator's designee at each study visit for any continuing AEs or new AEs since the previous visit. The subject will be asked to return to the site for an unscheduled visit if an AE occurs between study visits, and if, in the opinion of the Investigator, the AE requires a study visit for full evaluation. Any AE reported by the subject or noted by the Investigator or the Investigator's designee will be recorded within the eCRF. The following information will be recorded for each adverse event: description of the event, date of onset and resolution, severity as assessed by the Investigator according to the "Guidance for Industry: Toxicity Scale for Healthy Adult and Adolescent Volunteers Enrolled in Preventive Vaccine Trials" ([Appendix 2](#)), causal relationship to study medication, outcome, and any treatment given.

Adverse events that are not serious and are ongoing at the subject's last visit will be followed for a maximum of 30 days. Serious adverse events that are not resolved or stabilized during this time period will be followed until resolution or stabilization.

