9. SAFETY MONITORING AND ADVERSE EVENTS

9.1. Treatment-Emergent Adverse Events (TEAEs)

Data regarding TEAEs will be collected in this study. TEAEs are events that are not present prior to study medication injection or, if present prior to study medication injection, have worsened in severity.

The reporting period for AEs starts after the injection of study medication on Day 1 and ends after the final study visit.

Definition of Adverse Events:

Adverse events in the eCRF will be classified according to the most recent US FDA definitions and in a manner consistent with ICH guidelines. As such the following definitions will be used:

An adverse event (AE) is any unfavorable and unintended sign, symptom, or disease temporally associated with the use of an investigational (medicinal) product (IP) or other protocol-imposed intervention, regardless of attribution. An AE may include intercurrent illnesses or injuries that represent an exacerbation (increase in frequency, severity, or specificity) of preexisting conditions (e.g., worsening of asthma).

The Investigator must report all laboratory results that are BOTH outside the normal range for the laboratory or has a toxicity grade of 1 or greater AND, in the opinion of the Investigator, are clinically significant. If any abnormal, clinically significant laboratory measure is found after informed consent but prior to study medication injection, the subject is to be excluded. If it is found after study medication injection, it should be reported as an AE.

Whenever possible, it is preferable to record a diagnosis as the AE term rather than a series of symptoms relating to a diagnosis. In order to classify AEs and diseases, preferred terms will be assigned by the Sponsor to the original terms entered on the eCRF, using the Medical Dictionary for Regulatory Activities (MedDRA).

The Investigator will assess AEs for severity utilizing the “Guidance for Industry: Toxicity Scale for Healthy Adult and Adolescent Volunteers Enrolled in Preventive Vaccine Trials”. This toxicity scale is presented in [Appendix 2](#). Laboratory values not listed on the toxicity scale will be assessed for severity by the clinical Investigator.

All adverse events that occur during this trial will be considered related to the study treatment.

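### TEAE tables have no onset-time breakdown after a single injection, so an early excess in a common term or in the any-TEAE row is diluted by later background events

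*SAP*

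**What the plan says.** SAP 7 sets two reporting periods for safety. For the interim, "The interim report will include all available safety information up to and including Week 26". For the end of the study, "The final report will include a cumulative assessment safety".

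Within those periods SAP 7.1 plans, by treatment group:
- an overview table of subjects "experiencing TEAEs by seriousness and toxicity grade severity", with the investigator's opinion on relatedness shown for information;
- a MedDRA table: "TEAEs will also be summarized by MedDRA system organ class and preferred term, including the number of TEAEs", together with the count and percentage of distinct subjects;
- subject-level listings of serious and non-serious TEAEs.

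Neither document plans a TEAE table by time of onset, by target knee versus elsewhere, or for local reactions as a group. By contrast, SAP 7.2 and 7.3 compare laboratory values and vital signs with baseline visit by visit.

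On collection, Protocol 9.1 says "The reporting period for AEs starts after the injection of study medication on Day 1 and ends" after the final visit. Protocol 5.1 lists the items recorded for each event, among them "description of the event, date of onset and resolution". It lists no field for side or joint.

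**The concern.** Exposure is a single injection into one knee (Protocol 3.3.2), and follow-up is a year. A reaction to the drug or the procedure would most naturally appear early. The arms also differ in vehicle: Protocol 8.1 describes the active product as suspended in a diluent with carboxymethylcellulose and polysorbate 80, while placebo is buffered saline. A cumulative table counts an event in week 1 and one in week 50 alike.

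The population has osteoarthritis, bilateral disease is allowed, and Protocol 3.3.1 reports musculoskeletal disorders as the most frequent class in Phase 1 (11/61 subjects). Later complaints under the same general terms are to be expected. Safety and tolerability, monitored through TEAEs, is a secondary objective. These tables are its main comparison between arms and are read without formal tests (Protocol 10.5.3), so their layout decides what a reader can see.

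**Working it through.** The plan gives no TEAE rate, power or margin, so there is no figure of its own to reproduce. The calculation below is an illustration on assumed rates. z is only a yardstick, because no safety test is planned.

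**Inputs**
- Arm size: 445/4 = 111.25, taken as n = 111 (SAP 2.1).
- Background: "28/61 subjects have reported 68 treatment emergent adverse events (TEAEs" (Protocol 3.3.1), so 28/61 = 45.9%. This pools active and placebo subjects, and cohort 3 was still blinded.
- Time over which that proportion accrued: not stated. Assumed T0 = 12 or 24 weeks.
- Effect: background rate doubled for the first 8 weeks, none afterwards. Both the doubling and the duration are assumptions. The duration is borrowed from the phrase "8-week toxicology studies (the approximate residence time of the drug" in Protocol 3.3.1.

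**Formulas**
- Rate λ = −ln(1 − 28/61)/T0 = 0.614/T0, which is 0.0512 per week (T0 = 12) or 0.0256 (T0 = 24).
- Subjects with at least one TEAE by week W: placebo pC = 1 − exp(−λW); dose pT = 1 − exp(−λ(W + min(W, 8))).
- z for subjects = (pT − pC)/√[pC(1 − pC)/n + pT(1 − pT)/n].
- Expected events: placebo EC = nλW; dose ET = nλ(W + min(W, 8)); z for counts = (ET − EC)/√(ET + EC), assuming Poisson counts.

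**Example, T0 = 12, Week 26.** pC = 1 − exp(−0.0512 × 26) = 73.6%. pT = 1 − exp(−0.0512 × 34) = 82.5%. The difference is 8.9 points and z = 1.6. Expected events are 147.8 and 193.2, an excess of 45.5, so z = 45.5/√341.0 = 2.5.

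**Any TEAE (T0 = 12 / T0 = 24)**

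| Cumulative to | Difference in subjects, points | z, subjects | z, event counts |
|---|---|---|---|
| Week 4 | 15.1 / 8.8 | 2.6 / 1.9 | 2.8 / 1.9 |
| Week 8 | 22.3 / 15.1 | 3.4 / 2.6 | 3.9 / 2.8 |
| Week 13 | 17.3 / 13.3 | 2.6 / 2.1 | 3.3 / 2.3 |
| Week 26 (planned) | 8.9 / 9.5 | 1.6 / 1.4 | 2.5 / 1.7 |
| Week 52 (planned) | 2.3 / 4.9 | 0.8 / 0.9 | 1.8 / 1.3 |

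The excess in events stays at about 45 (T0 = 12) or 23 (T0 = 24) from Week 8 on. Only the background grows. The subject proportion also saturates: with T0 = 12, 93% of placebo subjects have had a TEAE by Week 52. The count z is approximate, because Phase 1 events clustered within subjects: 68 were reported, against 0.614 × 61 = 37.5 expected if events were Poisson.

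**Musculoskeletal class, same formulas with 11/61.** The difference in subjects is 10.9 / 6.0 points at Week 8, 10.0 / 5.8 at Week 13, 8.1 / 5.2 at Week 26 and 5.2 / 4.2 at Week 52. The z at Week 8 is 2.1 / 1.5 and at Week 52 0.8 / 0.6. Dilution is milder because the background is lower.

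**The case against.** Safety in this Phase 2 trial is descriptive, and cumulative tables by class and term contradict nothing in either document. Several specific objections also have weight.

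- A reader might infer that TEAEs are shown by MedDRA term alone. They are not. The overview table splits by seriousness, grade and investigator relatedness, and Protocol 9.1 defines relatedness partly by timing and by attribution to the injection. This gives some separation from background. It is limited, because the split appears only in the overview table, is informational, and every event formally counts as related.
- A reader might infer that an early excess would vanish. The planned event counts do not saturate and keep more of the signal, as the last column of the table shows. A reaction coded to its own preferred term keeps its own row and is diluted little. Phase 1 musculoskeletal events alone fell under 5 preferred terms.
- A reader might infer that the drug is known to stay in the human knee for 8 weeks. The phrase is a parenthesis about the animal toxicology studies behind the Phase 1 starting dose. It supports 8 weeks as an illustrative window and no more.
- Target-knee pain is compared by arm through WOMAC pain from Week 4 onwards. That partly covers local pain, but not swelling or a reaction that has resolved before Week 4.
- Listings contain the detail, but they are not a by-arm comparison across some 445 subjects.

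These points reduce the size of the problem. None of them supplies a table by time of onset.

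**Conclusion.** The point holds for time of onset. Both planned summaries pool all events since injection, and an early excess in the any-TEAE row or under a common term such as joint pain is diluted by later events. Under the stated assumptions, the difference in subjects falls from 22 or 15 points at Week 8 to 9 or 10 by Week 26 and 2 or 5 by Week 52. Event counts lose less (z about 2.5 or 1.7 at Week 26, 1.8 or 1.3 at Week 52). The direction follows from the table layout. The size rests on an assumed constant background, an assumed Phase 1 follow-up time and an assumed doubling for 8 weeks.

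The location part is weaker. A reader might infer that a target-knee table can simply be built from data in hand. The documents do not support that: Protocol 5.1 lists no laterality field and the case report form is not among them. A split is possible only where the description names the joint.

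This is a worthwhile addition to the safety reporting. It is not a flaw in trial conduct or error control.

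**What to change.** In SAP 7.1, before the Week 26 unblinding, add by-arm TEAE tables by onset period, showing both subjects and events, overall and by system organ class and preferred term:
- Day 1 to Week 13 cumulatively, with Day 1 to Week 4 shown within it;
- after Week 13 to Week 26;
- after Week 26 to Week 52 (final report).

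Use as denominator the subjects still under observation in each period. Keeping Day 1 to Week 13 whole matters, because a cut at Week 4 alone would divide an 8-week excess between two tables. In the illustration the Week 13 table shows 17 or 13 points, against 15 or 9 in the Week 4 table.

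Where the recorded description identifies the joint, also show joint TEAEs as target knee, elsewhere or not stated, coded by staff blind to treatment.

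The cost is a few more descriptive tables and one blinded coding pass. Onset dates are already collected, so the onset tables need no change to trial conduct. The knee split may be incomplete, and the share not stated should be reported.
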